6.1.3 Descriptive analyses

The SPD of index lesions will be log10 transformed and the change from baseline of the log10 transformed SPD at the end of treatment (i.e. the Day 85 assessment for patients who complete the 12 week treatment period or the treatment discontinuation visit for patients who discontinue treatment prematurely prior to Day 85 visit) will be calculated for patients with baseline and end of treatment SPD measurements. A second endpoint will be derived as the sum of the square root of the products of diameters along with the change from baseline.

The change from baseline in naïve B cells out of total B cells at Day 29, Day 57 and Day 85 and the end of treatment (i.e. the Day 85 assessment for patients who complete the 12 week treatment period or the treatment discontinuation visit for patients who discontinue treatment prematurely prior to Day 85 visit) will be calculated for patients with baseline and the corresponding time-point measurements. Baseline will be defined as the arithmetic mean of the baseline and Day 1 values when both are available, and if either baseline or the Day 1 value is missing, the existing value will be used.

Descriptive summary statistics and individual patient profiles will be provided by age group, treatment and time point.

Commercially Confidential Information

6.1.4 Statistical model, assumptions and hypotheses

An analysis of covariance will be performed to compare the change of the log10 transformed SPD from baseline between the two treatment groups, with treatment as a fixed effect and log10 transformed baseline SPD as a covariate. The baseline intake of glucocorticoids as well as the information about being treated with intravenous immunoglobulin G (IgG) will both be included as categorical (Yes/No) covariates. The comparison of the two treatment groups will be two-sided, with a 5% type I error. Patients with zero lesions at baseline will be excluded from the analysis.

Commercially Confidential Information

An analysis of covariance will be performed to compare the change from baseline in the naïve B cells at the end of treatment (i.e. Day 85 assessment for patients who complete the 12 week treatment period or the treatment discontinuation visit for patients who discontinue treatment prematurely prior to Day 85 visit) between the two treatment groups, adjusted for baseline naïve B cells frequencies. The use of glucocorticoids and intravenous IgG at baseline will both be included as categorical (Yes/No) fixed effects. Comparison of the two treatment groups will be two-sided, with a 5% type I error. Only patients with a reduced percentage of naïve B cells at baseline (defined as below 48 % van Gent et al 2009) will be included to the analysis. Baseline

Commercially Confidential Information

6.1.4.1 Model checking procedures

Residual plots will be inspected to assess the adequacy of the model.

6.1.4.2 Handling of missing values/censoring/discontinuations

The inferential analyses of the lymphadenopathy will include only patients with baseline and end of treatment lymphadenopathy measurements. Also patients with zero lesions at baseline will be excluded from the primary and sensitivity analysis for lymphadenopathy.

The primary analysis of the naïve B cells will include only patients who have baseline and end of treatment naïve B cells measurements and who also have a reduced percentage of naïve B cells at baseline (defined as below 48 % van Gent et al 2009).

6.1.4.3 Graphical presentation of results

Model estimated mean (SE) profiles and individual patient profiles will be provided by treatment and age group.

For the individual patient profiles using the PD analysis set all data will be displayed but the lines will be solid up to the treatment discontinuation +14 days and for subsequent time points the line will be dotted.

6.2 Secondary objectives

All subjects within the secondary efficacy analysis (efficacy parameters other than those used for primary objectives) will be included in the secondary efficacy data analysis where not otherwise specified. The rules as detailed in [Section 6.1.4.2](#) regarding discontinuation and treatment withdrawal will also be followed for the secondary efficacy parameters.

6.2.1 Estimands

Commercially Confidential Information

6.2.2 Variables

Short form 36 Survey (SF-36)

SF-36 in this study is to assess the physical and mental functioning of patients.

The SF-36 is a widely used instrument to measure generic health status. It is a 36-item questionnaire that has proven useful in monitoring generic and specific populations, comparing the relative burden of different diseases, differentiating the health benefits produced by different treatments, and in screening individual patients.

The SF-36 measures the impact of disease on overall quality of life and consists of eight subscales (physical function, pain, general and mental health, vitality, social function, physical and emotional health) which can be aggregated to derive a physical-component summary score and a mental-component summary score.

Work Productivity and Activity Impairment (WPAI) plus Classroom Impairment (CIQ) Questionnaire

The WPAI in this study measures the amount of absence or presence and daily activity impairment attributable to APDS/PASLI. As younger patients (age 12 and above) may also be enrolled in the study the WPAI-CIQ version of the questionnaire will be used for all patients as it also measures the amount of absence or presence for school attendance and daily classroom activity impairment attributable to APDS/PASLI.

Patient Global assessment (PtGA) Questionnaire

The patient's global assessment questionnaire asks patients about their APDS related well-being using 100 mm visual analogue scale (VAS) ranging from "very poor" (0) to "very good" (100).

Physician's Global assessment (PGA) Questionnaire

In the physician's global assessment questionnaire the Investigator rates the disease activity of their patient using 100 mm VAS ranging from "no disease activity" (0) to "maximal disease activity" (100).

To enhance objectivity, the physician must not be aware of the specific patient's global assessment, when performing his own assessment on that patient.

Imaging Data

The MRI/CT images will be analyzed by VirtualScopics as described in the imaging charter. The following quantitative and qualitative measurements will be summarized.

- Sum of product of diameters of the index lesions and percent change in sum of product of diameters relative to baseline
- 3D volume of index and measureable non-index lesions
- Presence of newly appearing lesions
- Liver volume and bi-dimensional size
- Spleen volume and bi-dimensional size
- Qualitative assessment of splenomegaly and hepatomegaly

6.2.3 Descriptive analyses

The change from baseline of SF-36 and WPAI-CIQ summary scores, and of visual analogue scale scores for PGA and PtGA, will be calculated and summary statistics will be provided by age group, treatment and visit. Mean (SD) profiles and individual profile plots will be provided by age group and treatment.

Summary statistics by age group, treatment and visit will be provided for the change from baseline in High Sensitivity C-reactive protein (hsCRP), Lactate dehydrogenase (LDH), beta2 microglobulin, ferritin, fibrinogen and erythrocyte sedimentation rate (ESR). Treatment with glucocorticoid drugs (e.g., prednisolone) can have an effect on these parameters and product, dose and timing of such treatment will be captured. Appropriate information needed for

interpretation will be added to the outputs as footnotes as required. Mean (SD) and individual profile plots will be provided by age group and treatment.

The 3D volume of index lesions will be log10 transformed and the change from baseline of the log10 transformed 3D volume at the end of treatment (i.e. the Day 85 assessment for patients who complete the 12 week treatment period or the treatment discontinuation visit for patients who discontinue treatment prematurely prior to Day 85 visit) will be calculated for patients with baseline and end of treatment measurements. Individual profile plots and summary statistics will be provided by age group and treatment.

6.2.4 Statistical model, assumptions and hypotheses

An analysis of covariance will be performed for SF-36 and WPAI-CIQ scores, and of visual analogue scale scores for PGA and PtGA, to compare the change from baseline at the end of treatment (i.e. the Day 85 assessment for patients who complete the 12 week treatment period or the treatment discontinuation visit for patients who discontinue treatment prematurely prior to Day 85 visit) between the two treatment groups, with treatment as a fixed effect and baseline as a covariate. The use of glucocorticoids and intravenous IgG at baseline will both be included as categorical (Yes/No) fixed effects. Comparison of the two treatment groups will be two-sided, with a 5% type I error.

The change from baseline will also be analyzed using a longitudinal mixed model, with treatment, time (as categorical), treatment by time, baseline and baseline by time interaction as fixed effects. The use of glucocorticoids and intravenous IgG at baseline will both be included as categorical (Yes/No) fixed effects. For patients who complete the treatment period, this repeated measures analysis will include all measurements in the treatment period (Baseline, Day 29, Day 57 and Day 85). An unstructured covariance matrix will be fitted to adjust for correlations among the measurements made on the same patient. The difference between the treatment groups in the change from baseline after 12 weeks of treatment will be assessed at two-sided 5% significance level.

An analysis of covariance will be performed for the 3D volume of index and measureable non-index lesions and 3D volume and bi-dimensional size of spleen to compare the change of the log10 transformed value from baseline between the two treatment groups, with treatment as a fixed effect and baseline as a covariate. The use of glucocorticoids and intravenous IgG at baseline will both be included as categorical (Yes/No) fixed effects. Comparison of the two treatment groups will be two-sided, with a 5% type I error.

Commercially Confidential Information

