11.5 Analysis of secondary and exploratory variables

11.5.1 Efficacy / Pharmacodynamics

In Part I

The changes from baseline of SF-36 and WPAI-CIQ summary scores, and of visual analogue scale scores for PGA and PtGA, were calculated and summary statistics were provided by visit.

Summary statistics by treatment and visit were provided for the change from baseline in High Sensitivity C-reactive protein (hsCRP) and Lactate dehydrogenase (LDH).

The SPD of index lesions will be log10 transformed and the change from baseline of the log transformed SPD at the end of treatment were calculated for all patients. Summary statistics for the change from baseline of the log10 transformed SDP were provided.

The non-index lesions were analyzed as per the Cheson criteria ([Cheson et al 1999](#)) described in the imaging manual.

In Part II

The change from baseline of SF-36 and WPAI-CIQ scores, and of visual analogue scale scores for PGA and PtGA, will be calculated and summary statistics will be provided by treatment and visit. An analysis of covariance will be done to compare the change from baseline at the end of treatment (i.e. the Day 85 assessment for patients who complete the 12 week treatment period or the treatment discontinuation visit for patients who discontinue treatment prematurely prior to Day 85 visit) between the two treatment groups, adjusted for baseline value. Comparison of the two treatment groups will be two-sided, with a 5% type I error. The change from baseline will also be analyzed using a longitudinal mixed model, with treatment, time, treatment by time, baseline and baseline by time interaction as fixed effects. For patients who complete the treatment period, this repeated measures analysis will include all measurements in the treatment period (Baseline, Day 29, Day 57 and Day 85). For patients who discontinue treatment prematurely only data up to and including the last planned visit prior to discontinuation will be included in the analysis. Data collected at the treatment discontinuation visit and thereafter will be excluded. An unstructured covariance matrix will be fitted to adjust for correlations among the measurements made on the same patient. The difference between the treatment groups in the change from baseline after 12 weeks of treatment will be assessed at two-sided 5% significance level.

Summary statistics by visit will be provided for the change from baseline hsCRP, LDH, beta2 macroglobulin, ferritin, fibrinogen and ESR.

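### Do the SAP's extra covariates and missing discontinuation rule for the Physician's Global Assessment (PGA) call for a change to the plan?

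*SAP*

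**What the plan says.** Protocol 2.2 labels PGA a key secondary endpoint for Part II. Protocol 11.5.1 gives it two analyses. The first is an analysis of covariance of change at end of treatment, "between the two treatment groups, adjusted for baseline value". The second is a longitudinal mixed model "with treatment, time, treatment by time, baseline and baseline by time interaction as fixed effects". For patients who stop treatment early, the mixed model is restricted: "only data up to and including the last planned visit prior to discontinuation will be included in the analysis", and "Data collected at the treatment discontinuation visit and thereafter will be excluded".

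SAP 6.2.4 keeps both analyses. To each it adds the sentence "The use of glucocorticoids and intravenous IgG at baseline will both be included as categorical (Yes/No) fixed effects". On which data enter the mixed model, it speaks only of completers: "For patients who complete the treatment period, this repeated measures analysis will include all measurements in the treatment period".

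SAP 6.2 says that the rules of 6.1.4.2 "regarding discontinuation and treatment withdrawal will also be followed for the secondary efficacy parameters". Section 6.1.4.2 opens with "The inferential analyses of the lymphadenopathy will include only patients with baseline and end of treatment lymphadenopathy measurements". It then excludes patients with no lesions at baseline, requires baseline and end-of-treatment naïve B cell values, and limits that analysis to patients below 48% at baseline.

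**The concern.** SAP 1.1 presents the document as implementing the Protocol's analysis, yet its PGA models contain two terms that the Protocol does not list for PGA. No readable note records a departure. With about 30 patients, two covariate sets can give different p-values from the same data.

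The second worry is an off-treatment value. Under Protocol 3.1.2, a patient who stops before V104 is asked to return at Day 85, and Day 85 is a mixed-model time point. An analyst working from the SAP alone would follow the pointer to 6.1.4.2, find no rule, and might keep that value. The Protocol would drop it. If the drug effect fades after stopping, the estimated treatment difference would shrink. PGA is the most prominent secondary result, so this deserved a check.

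**Working it through.** **Side by side (readable text)**

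| Item | Protocol | SAP (Part II) |
|---|---|---|
| PGA covariance analysis, covariates | Baseline (11.5.1) | Baseline, glucocorticoids, IV IgG (6.2.4) |
| PGA mixed model, extra covariates | None listed (11.5.1) | Glucocorticoids, IV IgG (6.2.4) |
| Co-primary models | Baseline, glucocorticoids, IV IgG (11.4.2) | Same (6.1.4) |
| End of treatment | Day 85, or the discontinuation visit for early stoppers | Same |
| Discontinuers in the mixed model | Discontinuation visit and later data excluded (11.5.1) | Silent |

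The SAP carries the co-primary covariates over to the secondary models. The same addition applies to PtGA, SF-36, WPAI-CIQ and the imaging secondaries, so it is a general modelling choice and not one aimed at PGA. On discontinuers the SAP is silent; it states no contrary rule.

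**Plan's own figure.** There is none for PGA. Protocol 11.7 gives power for key secondary variables as not applicable. All effect sizes below are assumptions, in SD units.

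**Cost of the two covariates in degrees of freedom.** There are 20 and 10 patients (Protocol 11.6). Residual degrees of freedom are 30 − 3 = 27 with intercept, treatment and baseline, and 30 − 5 = 25 with the two extra terms. The two-sided 5% critical t moves from 2.052 to 2.060. Noncentrality = effect / √(1/20 + 1/10) = effect / 0.387, with equal residual SD.

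| Assumed effect | Power, 27 df | Power, 25 df |
|---|---|---|
| 0.8 | 51.3% | 51.0% |
| 1.0 | 70.2% | 69.9% |
| 1.2 | 84.8% | 84.6% |

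The loss is 0.2 to 0.3 percentage points.

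**Do the two covariance models disagree?** Simulation: 20:10, complete data, 6,000 runs per setting. Covariate prevalences are 0.5 and 0.6. Effects are 1.04, 0.91 and 0.68 SD at baseline-to-follow-up correlations of 0.4, 0.6 and 0.8. At correlation 0.6:

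| Each covariate shifts PGA by | Different verdict at p = 0.05 | Power, Protocol set | Power, SAP set |
|---|---|---|---|
| 0 SD | 6.6% | 78.6% | 75.6% |
| 0.3 SD | 8.4% | 76.6% | 75.9% |
| 0.5 SD | 12.2% | 72.8% | 75.5% |

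Over all three correlations the disagreement is 6.4% to 16.9%, and with no true effect 2.1% to 4.5%. A separate rerun at correlation 0.6 gave 6.8%, 9.2% and 12.5%. The 3-point power drop in the first row is mostly chance covariate imbalance between small arms. At the same effect (0.91 SD), degrees of freedom alone take power only from 80.8% to 80.6%.

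**What if the Protocol's discontinuer rule were overlooked?** Simulation: mixed model with SAP covariates, correlation 0.6, true effect 1 SD, stopping day uniform on 2 to 57, effect wholly lost off drug, 1,500 runs. Shrinkage = 1 − (estimate with off-treatment Day 85 kept) / (estimate under the Protocol rule).

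| Discontinuation | Estimates | Shrinkage | Power |
|---|---|---|---|
| 5% | 1.001 vs 0.949 | 5% | 84.2% vs 79.9% |
| 10% | 1.002 vs 0.902 | 10% | 80.6% vs 73.7% |
| 20% | 0.985 vs 0.786 | 20% | 73.9% vs 59.3% |

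If half the effect is kept, shrinkage is about 2.5%, 5% and 9%. With no discontinuation it is zero; all 6 Part I patients completed treatment (Protocol 3.2.2). These figures show the cost of disregarding a written Protocol rule, not the plan's expected behaviour.

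**Would any repair change a result?** Recording the covariates as a departure keeps the SAP model. Repeating the discontinuer rule in the SAP restates what Protocol 11.5.1 already requires. Naming a main PGA analysis would write down an ordering that redacted text may already hold. Both documents put the covariance analysis first and introduce the mixed model as an additional analysis.

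**The case for a change.** The strongest case for a change is that the two documents list different terms for the endpoint they single out. Protocol 11.5.1 words the mixed model as a list of fixed effects, which reads as complete. If an analyst chose between covariate sets after unblinding, the chance that at least one was significant under no effect would be 5.5% to 7.2% in the simulation. The cross-reference in SAP 6.2 names 6.1.4.2, which carries no redaction, so nothing hidden elsewhere makes that pointer correct. Nor would adding the exclusion sentence from Protocol 11.4.3 suffice: it drops data after the discontinuation visit, whereas 11.5.1 drops that visit too. The repair would cost only a few sentences.

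The mismatch and the faulty pointer stand. The consequence does not. The later, more detailed document fixes one covariate set, so no choice is left open. SAP silence on discontinuers does not repeal the Protocol's rule. The estimand sections (SAP 6.1.1 and 6.2.1) and the end of 6.2.4 are redacted and may restate it. A change note may likewise lie in redacted or removed pages, so its absence cannot be shown. Protocol 11.7 concerns power only and does not settle whether the PGA p-value is formal or nominal.

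**Conclusion.** No change to the plan follows. The added covariates are a sensible elaboration that aligns the secondary models with the co-primary ones. The gap on discontinuers is one that an analyst holding both documents fills from Protocol 11.5.1. The cross-reference is a clerical slip. Correcting it and noting the covariates would be good housekeeping for all the affected secondary endpoints, but no planned estimate or test would differ.

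The cost of the extra terms is about 0.3 percentage points of power through degrees of freedom. Including chance imbalance, it ranges from a loss of about 3 points to a gain of about 3 points at correlation 0.6, depending on how strongly the covariates relate to PGA. The discontinuer question concerns only the mixed model and has no effect if nobody stops early.

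This conclusion assumes that the SAP was final before unblinding, that the Protocol governs where the SAP is silent, and that the redacted text does not contradict either. The simulated figures rest on prevalences, effects and discontinuation rates that the documents do not give. The co-primary analyses are not involved.

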2.2 Secondary objective(s)

Objective	Endpoint

 Part II: To assess the effect of CDZ173 on lymphadenopathy (non-index lesions and spleen) 	
 MRI/CT imaging – e.g. 3D volume of index and measurable non-index lesions selected as per the Cheson methodology, and 3D volume and bi-dimensional size of the spleen

 Part I and II: To assess the pharmacokinetics of CDZ173 in patients with APDS/PASLI 	
 Single dose CDZ173 PK parameters (including but not limited to Cmax and AUC) and trough evaluations after multiple dose

 Part I and II: To assess the efficacy of CDZ173 to modify health-related quality of life in patients with APDS/PASLI 	
 SF-36 (Short Form 36) Survey and WPAI-CIQ (Work Productivity Activity Impairment plus Classroom Impairment Questionnaire)

 Part I and II: To assess the efficacy of CDZ173 by the Physician's Global Assessment (PGA) and the Patient's Global Assessment (PtGA) 	
 Visual analogue scales for PGA and PtGA (for Part II the PGA is a key secondary endpoint)

 Part I and II: To assess biomarkers reflecting the efficacy of CDZ173 to reduce systemic inflammatory components of the disease 	
 C reactive protein (CRP), Lactate dehydrogenase (LDH) For Part II additional: beta2 microglobulin, ferritin, fibrinogen and erythrocyte sedimentation rate (ESR)

 Part I and II: To assess the treatment benefit to individual patients 	
 Narratives

 Part II: To assess the safety and tolerability of CDZ173 in patients with APDS/PASLI 	
 All safety parameters, including AEs, physical exam, vital signs, ECG, safety laboratory (hematology, blood chemistry, urinalysis)

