11.7 Power for analysis of key secondary variables

Not applicable.

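### Does calling PGA a key secondary endpoint require a gate from the co-primaries and one named deciding model?

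*SAP*

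**What the plan says.** The endpoint column of Protocol 2.2 carries the label: "for Part II the PGA is a key secondary endpoint". The synopsis and SAP 1.3.1.2 list PGA among the secondary objectives without it. Protocol 11.7, headed "Power for analysis of key secondary variables", is marked not applicable.

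Protocol 11.5.1 and SAP 6.2.4 (Part II) both specify, for SF-36, WPAI-CIQ, PGA and PtGA, an ANCOVA of the change from baseline at end of treatment, two-sided 5%. End of treatment means Day 85 for completers and the discontinuation visit for patients who stop earlier. Both then add a second model: "The change from baseline will also be analyzed using a longitudinal mixed model". In the SAP its test reads: "The difference between the treatment groups in the change from baseline after 12 weeks of treatment will be assessed at two-sided 5% significance level". Lesion and spleen measures get the ANCOVA only.

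For patients who stop early, Protocol 11.5.1 limits the mixed model to planned visits before discontinuation: "Data collected at the treatment discontinuation visit and thereafter will be excluded". SAP 6.2.4 speaks of completers only: "For patients who complete the treatment period, this repeated measures analysis will include all measurements in the treatment period". SAP 6.2 says that the rules of 6.1.4.2 "regarding discontinuation and treatment withdrawal will also be followed for the secondary efficacy parameters". Section 6.1.4.2 sets conditions for which patients enter the co-primary analyses, for example "The inferential analyses of the lymphadenopathy will include only patients with baseline and end of treatment lymphadenopathy measurements", and has no visit rule.

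SAP 6.2.1 (secondary estimands) is wholly redacted. SAP 6.1.1, parts of 6.1.4, the end of 6.2.4, Protocol 11.4.4 and part of the synopsis data-analysis row are also redacted.

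**The concern.** In a trial whose Part II the protocol calls confirmatory (11.4), a reader expects a key secondary endpoint to have a defined place: one analysis that decides it, and a rule for when it may be tested. In the readable text the label has no such effect. PGA is tested at the same level as PtGA or SF-36, twice, by models that treat early stoppers differently: the ANCOVA uses the discontinuation visit and the protocol's mixed model drops it.

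The SAP's cross-reference makes this look worse, because an analyst who follows it to 6.1.4.2 finds no visit rule. Patients who stop before V104 are asked to come back at Day 85, so an off-treatment Day 85 PGA value can exist, and someone reading the SAP alone might include it.

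At stake would be which number is the PGA result, whether it could be claimed after a failed co-primary, and some extra false-positive risk if the better of two p-values were chosen. With about 30 patients, the two models can fall on opposite sides of 5%.

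**Working it through.** **1. The plan's own figures.** The documents give no power or error rate for PGA. The nearest figures are in Protocol 11.6: 98% power for naïve B cells with 27 patients (difference 25 points, SD 14), and joint co-primary power of at least 78%.

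- At 2:1, 27 patients split 18:9. Noncentrality = 25 / (14 × √(1/18 + 1/9)) = 25 / 5.715 = 4.37. Power is 98.7% by noncentral t (25 df) and 99.2% by the normal formula. The stated 98% is reproduced.
- Joint power: 0.98 + 0.80 − 1 = 0.78. This matches if SPD power is 80%, which is an assumption because those inputs are redacted.
- A gate on both co-primaries would therefore be closed in up to 1 − 0.78 = 22% of trials under the design assumptions.

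**2. Counting either PGA model as success, no true effect.** The rate is 0.05 + 0.05 − P(both significant), which depends on the correlation of the two test statistics. A simulation (4,000 trials per setting, 20:10, visit correlation 0.5, SAP covariates, protocol visit rule) gave these correlations at assumed discontinuation rates:

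| Discontinuation | Correlation | Either significant, bivariate normal | Either significant, simulated |
|---|---|---|---|
| 0% | 0.98 | 5.9% | 5.8% |
| 5% | 0.96 | 6.3% | 6.1% |
| 10% | 0.93 | 6.7% | 7.3% |
| 20% | 0.87 | 7.3% | 7.2% |

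Monte Carlo error is about 0.4 points. A separate simulation with a different visit correlation pattern (2,000 trials per setting) gave 5.9%, 6.6% and 7.1% at 0%, 10% and 20%. By the normal calculation, the excess over 5% is 0.9 to 2.3 points.

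**3. How often the two models disagree.** With no effect they disagree on significance in 1.6%, 3.0% and 4.3% of trials at 0%, 10% and 20% discontinuation (second simulation). With an assumed effect of 1.05 SD (ANCOVA power 81% falling to 73%), disagreement is 3.9%, 6.9%, 10.6% and 14.9% at 0%, 5%, 10% and 20% (first simulation). The documents give no PGA effect, SD or discontinuation rate. All six Part I patients completed treatment, but six is too few to exclude these rates: the one-sided 95% upper limit is 1 − 0.05^(1/6) = 39%.

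**4. All secondary tests together.** The readable text names eight measures tested at 5%. If they were independent, the chance of at least one false positive is 1 − 0.95^8 = 33.7%. At pairwise correlation 0.9 it is 11.9%. This matters only if any one of them could support a claim, and no readable text says so.

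**5. The visit rule, side by side.** Protocol 11.5.1 is explicit. SAP 1.1 says that the SAP carries out the analysis planned in the protocol, and SAP 1.2 ties it to protocol v10. SAP 6.2.4 repeats the protocol's mixed model, leaves out the sentences on early stoppers and puts nothing contrary in their place. The off-treatment Day 85 value has no stated use elsewhere in the PGA analysis either: the ANCOVA takes the discontinuation visit. For the co-primaries, Protocol 11.4.3 bars data after that visit. Keeping the Day 85 return value in the mixed model is a rule that neither document states.

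**6. Covariates.** Protocol 11.5.1 adjusts the PGA ANCOVA for baseline only, and SAP 6.2.4 adds glucocorticoid and IgG use. The SAP version mirrors the co-primary ANCOVA and is the more detailed text. Either comparison is valid under randomisation, and the two extra terms cost two degrees of freedom.

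**The case for a change.** The best case for a change is that only one secondary endpoint was singled out, and that Protocol 11.5.1 shows no redaction in its Part II text. Even if a hierarchy lies behind the SAP's redactions, the protocol itself has none. Ranking the models, copying the visit rule and adding a gate would take a few sentences, no patients and no alpha from the co-primaries. The word introducing the mixed model hints that the ANCOVA leads, but that is inference, and a disagreement rate of up to 15% is not negligible.

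Part of this stands. The readable text does not rank the models, the SAP 6.2 cross-reference leads to no visit rule, and the label has no stated effect.

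It does not amount to a needed change. The ANCOVA is listed first, uses the same end-of-treatment definition as the co-primaries and is the co-primary method, so a statistician would report it as the main PGA result with the mixed model in support. Disagreement between two prespecified models would be visible, because both are planned. The silence of the synopsis and SAP 1.3.1.2 is weak evidence of inconsistency: those entries list objectives, whereas the label belongs to an endpoint. Protocol 11.7 concerns power, not testing order. The gate is a choice that depends on whether a PGA claim is intended, which the readable documents do not say. If none is intended, deleting one word would serve equally well, so the gap is in labelling and not in the analysis.

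**Conclusion.** No change is needed. This is a gap that analysts fill sensibly: ANCOVA as the main PGA result, mixed model as support, and the protocol's visit rule for early stoppers. Followed as written, the plan yields two sound prespecified PGA analyses and leaves the co-primary conclusion untouched.

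The size is small. Taking the better of the two models would cost about 1 to 2 points of type I error (5.9% to 7.3% instead of 5%), and no readable text adopts that success rule. Model disagreement of roughly 4% to 15% rests on an assumed 1.05 SD effect and assumed discontinuation of 0% to 20%. The 12% to 34% familywise figures apply only if every secondary measure could support a claim.

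The conclusion covers the readable text only. The redacted parts, SAP 6.2.1 and the end of 6.2.4 among them, may already contain a hierarchy or a discontinuation rule, so its absence from the plan cannot be asserted. The question would carry more weight if the sponsor meant to make a formal PGA claim and the redacted text held no testing order.
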